3.7 Identification of the Medical Device

The medical device will be labeled for clinical investigation use only. The label includes the address of the legal manufacturer and all other essential information to allow full traceability of the medical device as per the regulatory labeling requirements.

3.8 Instructions for Use

Device Instructions for Use are available as a separate document to study personnel. Printed instructions for Use are handed to study participants along with the device. Electronic version of IFU is accessible from the Application at any time. A brief description of principle of operation can be found in sections 3.1, 3.4 above.

3.9 Summary of Necessary Training

General instructions and training in device use as per the IFU will be provided to study participants at the participating sites. No specific skills are required from study participants beyond basic level of experience with general purpose Android applications. Training will be delivered by designated study personnel and will be recorded in a corresponding CRF. In addition,

records of the training session will be recorded in the study DB with label “training”. The criteria for training effectiveness will be ability of the participant to run a training treatment session independently. At the end of the session, the device will be switched into operational mode by “sliding off” training mode indicator on the main screen of the application.

Training to the investigator and staff will be delivered by Theranica representative in a frontal session including demo and training activations. In order to provide additional support to clinical personnel, a training clip was recorded and will be available at all training sessions for staff and participants.

4 PRELIMINARY INVESTIGATIONS AND JUSTIFICATION FOR THE STUDY DESIGN

4.1 Previous Pre-Clinical Experience

There were no animal studies with the Nerivio Migra device. Since it is applying energy output similar to that of FDA approved TENS devices, and in accordance with the application of risk management as per EN ISO14791, the necessity for such a study has been precluded. There is no valid animal model to test the effectiveness of this device.

4.2 Previous Clinical Experience

Theranica has completed a prospective, randomized, double-blind, sham controlled, cross-over, multiple treatment arms single center study **“Relief of migraine pain through electro stimulation”** at the Neurology Department, Rambam Medical Center (Haifa, Israel). A brief summary of this pilot study protocol is provided below, along with an overview of the procedures utilized and the results observed.

Pilot Study Objective

The purpose of the investigation was to evaluate the safety and performance of the Nerivio Migra for the treatment of non-chronic migraine patients with and without aura and provide comparative data regarding performance and tolerability of the evaluated treatment programs.

Inclusion and Exclusion Criteria

Inclusion Criteria

1. Adult male and female ages 18-75.
2. Patients meeting International Headache Society criteria for migraine with and without aura.
3. Patients reporting 2-8 migraine attacks per month.
4. Patient must be able and willing to comply with the required follow-up schedule
5. Patient must be able and willing to provide written informed consent
6. Patient was not on preventive medications for at least two months

Exclusion Criteria

1. Has other significant pain problem (e.g. cancer pain, fibromyalgia or other head or facial disorder) that in the opinion of the investigator may confound the study assessments

2. Has severe cardiac or cerebrovascular disease.
3. Has uncontrolled high blood pressure (systolic > 160 mmHg, diastolic > 100 mmHg after 3 repeated measurements within 24 hours).
4. Is currently implanted with an electrical and/or neurostimulator device (e.g. cardiac pacemaker or defibrillator, vagus nerve neurostimulator, deep brain stimulator, spinal stimulator, bone growth stimulator, cochlear implant, Sphenopalatine ganglion stimulator or Occipital nerve stimulator).
5. Known epilepsy.
6. Use of Cannabis including medical use.
7. Has chronic migraine (more than 15 headache days per month).
8. Has undergone nerve block (occipital or other) in the head or neck within the last 2 months.
9. Has received Botox injections within the last 6 months.
10. Is pregnant or thinking of becoming pregnant during the study period, or of childbearing years and is unwilling to use an accepted form of birth control.
11. Is participating in another clinical study in Migraine treatment or prevention.
12. Does not possess the basic cognitive or motor skills needed to operate android cell phone.

Study Procedures

Potential patients signed informed consent prior to any study procedure. The patient medical history, migraine history, use of concomitant medications and diagnosis were recorded. Patients found eligible by meeting all of the inclusion criteria and none of the exclusion criteria received documented training whereupon its successful completion the investigational device was provided to study participants for home use.

As per the instructions for use, participants were instructed to activate the device at the onset of a migraine attack and manually adjust stimulation intensity to a level where it is perceivable but not painful. Patients were requested to refrain from use of rescue medications prior to and during the first two hours following treatment by the device, and if they could not comply with this, record medications usage in the smartphone application.

Five 20-minute long stimulation protocols were programmed into each unit; four active programs at 100-120 Hz, with primary phase widths of 200 (P200), 150 (P150), 100 (P100) and 50 (P50) microseconds, and one placebo stimulation protocol (P0) at 0.1 Hz frequency with 45 microseconds long pulses. Stimuli were given at random sequences with the following distribution: P0 and P200: probability of 1/3 each, P50, P100, P150: probability of 1/9 each. Randomized sequences of programs were generated independently for each participant.

Both patients and study personnel were blinded to the order of individual treatments.

Via the smartphone application, each participant was asked to rate his/her migraine pain level four times using a Numeric Pain Rating Scale (NPS, values 0-10): (1) upon starting the treatment, (2) during (halfway through treatment program), (3) at the end of treatment, as well as (4) two hours after treatment.

At the beginning of each treatment, participants were asked to provide feedback using the application regarding the time elapsed from start of migraine attack to start of the treatment. In case of failure to provide feedback regarding pain level post-treatment, telephone follow-up was performed by study investigator staff to solicit such feedback. Follow up phone calls were

performed to record changes in medical condition, concomitant medication, migraine therapy and adverse effects. Unscheduled visits were recorded and termination visit were scheduled upon the completion of the study as defined by a maximal number of 20 complete treatment cycles but no longer than 6 months from enrollment. (whichever is fulfilled first). In the event of premature discontinuation an early discontinuation visit was scheduled. End of study interview was performed soliciting feedback regarding device usability, burden of treatment, use of migraine medications during the study period, as well as free comments.

Study Endpoints

- The primary efficacy endpoint of the study was the proportion of responders, where a responder is defined as subject with clinically significant decrease in pain score measured by Numeric Pain Rating Scale (NPS) of at least 50% 2 hours post treatment as compared to baseline in at least 50% of treatments.
- The second primary performance endpoint was relative pain reduction at 2 hours post treatment as compared to baseline.
- The primary safety endpoint was evidence of device related adverse effects.

Burden of treatment was assessed by mean scores of post-study questionnaire. Success was defined as superior performance of active treatments as compared to sham treatment. The protocol provided for enrollment of up to 100 patients.

Summary of Results

The pilot study was performed between June 2015 and March 2016. A total of 86 participants were provided with the Nervio Migra devices for use as part of this clinical study.

A summary of participants' demographic characteristics is presented in Table 2 below.

	Female	Male
N (%)	69 (80%)	17 (20%)
Age mean (min-max, STD)	45.2 (22-72, 11.7)	48.8 (26- 67, 11.7)
Migraine attacks per month, mean (STD)	5.1 (2.7)	5.34 (2.3)
Mean pain intensity during attack	8.9	8.6
Occurrence of aura	40 (58%)	11 (65%)

Table 2 – Pilot Study Population

Seventy-two participants successfully treated at least one migraine attack. The remainder of participants either did not treat their attacks per protocol, or failed to provide complete feedback. One participant was excluded from statistical analysis due to repeated use of rescue medications concurrently with the electro stimulation treatments. Complete reporting was obtained for 70% of activations for P200, P150, P100 programs, 58% of activations of P50 and 28% of placebo activations.

No adverse events related to the device and no side effects were reported.

Observed outcome measures based on ITT analysis are summarized in Table 3 below.

	Sham	Active programs				Overall active programs (p vs. placebo)
		P0	P200	P150	P100	
%50% (% responders), N=71	26%	46% (0.04)	48% (0.06)	39% (0.4)	44% (0.14)	64% (significance level 0.005)
Relative pain reduction (%)	-2	-20 NS	-26 P=0.02	-16 NS	-18 NS	Model p=0.031
Pain grade reduction (% responders), N=57	24%	58% (0.02)	52% (0.08)	40% (0.44)	48% (0.20)	76% (significance level 0.005)
No pain after two hours (% responders), N=57	6%	30% (0.004)	12% (0.56)	23% (0.06)	26% (0.14)	44% (significance level 0.005)

Table 3 – Pilot Study Results

Our results show that remote electrical stimulation allowed to achieve significant reduction in the migraine pain. Analysis per pain grades, as has been used for triptans, shows results similar to the triptans per pain reduction and pain elimination. When taking all active stimulation protocols together, 64% of the patients had more than 50% pain reduction, in more than half of their treated attacks. Relative pain reduction for the active stimuli ranged between 16 and 26%, while for the placebo stimulation the reduction was of 2% only. Mean pain level at device activation point was 4.6. Overall ANOVA based effect was significant (p=0.031), with significant effect in post hoc analyses for the P150 protocol.

In terms of change in pain grades, reduction from moderate or severe to mild or none was reported by 58% of the participants in response to the strongest stimulation program (P200, widest pulse), as opposed to 24% for placebo. Overall, 76% of subjects reported such reduction to active stimulation (significant at 0.005 level vs. placebo). Reduction to no pain outcome occurred in more than 50% of activations for 30% of participants when the strongest program was activated, as opposed to 6% for placebo. In the course of the study, 64% of participants who provided feedback on at least one active program activation reported at least 50% pain reduction in more than half of their activations and are considered responders to the evaluated treatment. This is significantly higher than the 26% responder to placebo activations (p=0.005).

In the end-of-trial interviews, subjects indicated (i) Reduction in amount of migraine medications during study period (mean questionnaire score was 1.5, where 1 means “same amount”, 2 means “less”); (ii) overall burden of treatment was considered very low – mean score was 2.5 (between “neutral” and “not at all”); and (iii) the device and application were found easy to use by a majority of study participants (mean questionnaire score was 3.85 (between “easy” and “very easy”)).

4.3 Clinical Investigation Risks and Benefits

4.3.1 Anticipated Benefits

Theranica's pilot study demonstrated a significant effect of Nerivio Migra in alleviating migraine pain (see pilot study results above). It is anticipated that patients will experience similar effect under the setting of the current study.

Another known benefit to patients participating in such a study is the ability to learn more about their medical condition through the assessments that will be performed throughout the course of the study. Additionally, patients will be closely observed by the study staff throughout their participation in the study. Last, all assessments associated with the study, as well as the study device, are provided at no charge to the participants.

4.3.2 Risks and Adverse Effects

Technical characteristics and electrical output of Nerivio Migra device are similar to other known and approved for personal use TENS devices applying electrical stimulation for pain relief purpose (see Table 1). Safety of the Nerivio Migra has been extensively tested and confirmed through bench performance testing (see section 3.5.1) as well as throughout Theranica's pilot clinical study with the device. No device related adverse events were recorded in the course of the pilot study, and treatment was well tolerated by participants.

Current study design does not require application of electrical stimulation for unusually prolonged periods, or other circumstances where the use of the device has not yet been validated. Hence this protocol presents minimal risks to the subjects and adverse events are not anticipated beyond those reported for other TENS devices. Potential expected device side effects are listed in section 14.7.

No information is available for use of the Nervio Migra and pregnancy, so women who are pregnant are not eligible for inclusion in this study.

As discussed with the FDA at a Pre-submission meeting (September 2016), the proposed clinical study meets the criteria of a Non-Significant Risk (NSR) device study.

4.3.3 Risk Control and Mitigation

The following efforts will minimize risks to patients in the study:

- Conduct of the study following successful completion of extensive bench performance testing and careful risk analysis.
- Selection of investigators who are experienced and skilled in management of patients with migraine.
- Establishment of a training program for study staff members (investigators and coordinator) and use of tools that will ensure proper training to the patients for home use of the device.
- Clearly defining the inclusion and exclusion criteria such that only appropriate patients are enrolled in the study.

4.3.4 Risk-to-Benefit Rationale

We believe that the Nerivio Migra device holds great potential to provide an efficient and low risk treatment option to the population of migraine sufferers. Assessing the risks against the potential benefits of the use of the Nervio Migra for alleviating migraine pain, Theranica and the principal investigators (PIs) have determined that there is a high likelihood that the expected benefit may outweigh the risk in patients fulfilling the study eligibility criteria.

5 OBJECTIVES & HYPOTHESES

5.1 *Objective*

The study purpose is to demonstrate safety and effectiveness of the Nerivio Migra electro stimulation device for treatment of migraine attacks with and without aura.

5.2 *Hypothesis*

The hypothesis is that the electro stimulation delivered transcutaneously to the peripheral nervous system at onset of a migraine headache will abort the attack, as indicated by significant difference between proportions of responders to the sham control stimulation and the active treatment without unexpected device related adverse effects.

6 DESIGN OF THIS CLINICAL STUDY

6.1 *Description*

This is a prospective, randomized, double-blind, sham controlled multi-center clinical trial “Migraine Treatment with Nerivio Migra electro stimulation device”. The study will enroll up to 248 patients diagnosed with migraine with and without aura, per the inclusion and exclusion criteria. These patients will be individually and randomly assigned to either treatment group or control group. For sham control, short electrical pulses of amplitude range similar to that of the treatment programs will be administered at very low frequency (0.1-0.5 Hz). The rationale underlying selection of sham control settings is that, on the one hand, pulses are perceivable and the user is able to manipulate their intensity similarly to the case of treatment programs, while, on the other hand, no clinically relevant treatment is delivered, based on existing knowledge of parameters range of electro stimulation treatments [5-7, 18].

Following successful screening, enrollment interview and signing of informed consent, participants will be provided with an active Nerivio Migra or identically looking sham device and trained to perform treatment and provide feedback via the smartphone application. Ratio between treatment and control groups will be 1:1.

Baseline information including mean frequency and severity of migraine attacks, occurrence of other headaches, presence of ICHD-3 diagnostic criteria for migraine with and without aura and use of preventive and rescue medications will be recorded.

Investigational devices will be programmed in active or sham mode with a 1:1 ratio, in order to achieve the desired ratio between active and control groups sizes, stratified with by use of preventive medications.

Study flow is schematically presented in the figure below.

[figure not shown]

Figure 4. Study Design

Following enrollment, the study will be conducted in three stages.

Stage One. In stage one (roll-in phase) recruited participants will be reporting their migraine attacks per ICHD-3 diagnostic criteria, including presence of aura, using an electronic migraine diary installed on their smartphones. Duration of this phase is one month.

Stage Two. This will be the parallel arm treatment stage.

Participants will be instructed to activate the device at onset of a qualifying migraine attack and manually adjust stimulation intensity to a level within the pre-defined range where it is well perceived but not painful. A qualifying migraine attack shall be preceded by at least 48 hours of freedom from headache. Patients will be requested to refrain from use of rescue medications prior to and during the first two hours after treatment with the device, and if they can not comply with this, record their use of rescue medications (migraine specific drugs or other medications or therapies that may be used to treat pain, from a pre-specified list) in the mobile application.

Via the smartphone application, each participant will be asked to rate his/her migraine pain level three times using Pain Grades Scale (0 - no pain, 1- mild pain, 2- moderate pain, 3 – severe pain): (1) upon starting the treatment, (2) two hours after start of treatment, (3) 48 hours after start of attack. At the start of each treatment, participants will be also asked to provide time elapsed from start of migraine attack to start of the treatment. Participants will be also asked to provide feedback regarding their use of medication (migraine specific drugs or other medications or therapies that may be used to treat pain, from a pre-specified list), presence of nausea, photophobia and phonophobia, and treatment perception. After providing feedback at two hours

after start of treatment and in case of pain recurrence, participants will be allowed to re-treat the attack using Migra device.

Adverse events will be reported.

Duration of study participation for each patient will be up to three months, determined by one month of the roll-in stage followed treatment of four qualifying attacks over the course of two months (whichever is achieved first).

Post study questionnaire will include patient global impression of change [27], blinding and usability assessments.

Stage Three. This part will include open label extended treatment. Following the completion of the study by all subjects and the return of all study devices, subjects will be offered a 2-month period of using active device, at no cost.

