1 SYNOPSIS

Sponsor	Theranica Bioelectronics Ltd. [name]
Title	A prospective, randomized, double-blind, sham controlled multi-center clinical trial “Migraine Headache Treatment with Nerivio Migra neurostimulation device”
Investigational Device	Nerivio Migra neurostimulation device is intended for acute treatment of migraine headache with and without aura via delivery of transcutaneous electrical stimulation below pain threshold to patient upper arm at the onset a migraine pain. The level of generated stimuli is similar to other FDA approved electro stimulation devices. Nerivio Migra treatment is self-administered by the patient. It is intended to alleviate pain through conditioned pain modulation. The device is controlled by a dedicated smartphone application.

Study Design	
A prospective, randomized, double-blind, sham controlled multi-center trial. Ratio between treatment and control groups will be 1:1, stratified by center and use of preventive medications.
 
The study will be conducted in three stages.
 
Enrolled participants will be provided with an active Nerivio Migra or an identically looking sham device and trained to perform treatment and provide feedback via the smartphone application. Investigational devices will be programmed in active or sham mode with a 1:1 ratio, in order to achieve the desired ratio between active and control groups sizes. Following successful completion of device and application training, subjects will be discharged.
 
Stage One. Roll-in. Participants will be reporting their migraine attacks using an electronic migraine diary installed on their smartphones. Duration of this phase is one month.
 
Stage Two. Parallel arm treatment stage. Following successful completion of Stage 1, the application will be activated in treatment mode. Subjects will be asked to apply the device and administer treatment at onset of their migraine pain. Subjects will be reporting their feedback via the smartphone application. Duration of Stage Two will be determined by treatment of four attacks over the course of two months (whichever is achieved first).
 
Stage Three. Open label extended treatment. Following the completion of the study by all subjects and the return of all study devices, subjects will be offered a 2-month period of using active device, at no cost.

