Study Procedures	
Following successful screening, enrollment interview and signing of informed consent, participants will be provided with an active Nerivio Migra or identically looking sham device and trained to perform treatment and provide feedback via the smartphone application.
 
Baseline information including mean frequency and severity of migraine attacks, occurrence of other headaches, presence of ICHD-3 diagnostic criteria for migraine with and without aura and use of preventive and rescue medications will be recorded.
 
During roll-in stage, migraine status will be recorded and participants will be requested to complete a quality of life questionnaire.
 
Participants who successfully completed the roll-in stage will continue to the stage involving treatment of four qualifying migraine attacks. A qualifying migraine attack shall be preceded by at least 48 hours of freedom from headache. Participants will be instructed to activate the device at the onset of a qualifying migraine attack and manually adjust stimulation intensity to a level within the pre-defined range where it is perceivable but not painful. Patients will be requested to refrain from use of rescue medications prior to and during the first two hours after treatment with the device, and if they can not comply with this, record their use of medications in the smartphone application. Via the application, each participant will be asked to rate his/her migraine pain level using Pain Grades Scale with values 0-3 (no pain, mild, moderate, severe): (1) upon starting the treatment, (2) two hours after starting treatment, (3) 48 hours after start of the first treatment corresponding to current migraine attack. Participants will be also asked to provide feedback using the application regarding the time elapsed from start of migraine attack to start of the treatment. In addition, participants will be reporting their use of rescue medication and presence of nausea, photophobia, phonophobia and allodynia, as well as additional migraine symptoms.
 
In case of failure to provide feedback regarding pain level post-treatment, queries will be generated via EDC system and telephone follow-up will be performed by study investigator staff to solicit such feedback. After providing feedback at two hours post start of treatment and in case of pain recurrence, participants will be allowed to re-treat the attack using Migra device.
 
Adverse events will be reported.
 
Post study questionnaire will include patient global impression of change, blinding and usability assessments.

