6.4.2.1 Start attack/episode PRO feedback data

The screen provides for collection of the following data:

Item	Description	Control type	Values range
Current migraine pain level	Current migraine pain level in pain grade categories	Dropdown list	Mild (1), Moderate (2), Severe (3).

Time from onset of migraine pain	Time from onset of migraine pain	Dropdown list	under 10 minutes 10-20 minutes 20-60 minutes 1-2 hours 2-4 hours over 4 hours
Nausea	Presence of nausea	Radio buttons	Y/N
Sensitivity to light	Presence of photophobia	Radio buttons	Y/N
Sensitivity to sound	Presence of phonophobia	Radio buttons	Y/N
Increased skin sensation	Presence of allodynia	Radio buttons	Y/N

6.4.2.2 2h PRO

This feedback dialog appears 2h after the treatment program has started.

The screen provides for collection of the following data:

Item	Description	Control type	Values range
Current migraine pain level	Current migraine pain level in pain grade categories	Dropdown list	No pain (0), Mild (1), Moderate (2), Severe (3).
Medication	Whether rescue medication was taken	Radio buttons	Y/N
Medication name	Rescue medication	Dropdown list	From a pre-defined list
Nausea	Presence of nausea	Radio buttons	Y/N
Sensitivity to light	Presence of photophobia	Radio buttons	Y/N
Sensitivity to sound	Presence of phonophobia	Radio buttons	Y/N

Increased skin sensation	Presence of allodynia	Radio buttons	Y/N
Arm side where device was applied	Left or right arm	Radio buttons	L/R
Pain location (side)		Dropdown list	L R both
Additional feedback	Additional, free style feedback	Textbox	Free text, optional

6.4.2.3 48h PRO

The screen shall provide for collection of the following data:

Item	Description	Control type	Values range
Current migraine pain level	Current migraine pain level in pain grade categories	Dropdown list	No pain (0), Mild (1), Moderate (2), Severe (3).
Medication	Whether rescue medication was taken	Radio buttons	Y/N
Medication name	Rescue medication	Dropdown list	From a pre-defined list
Additional feedback	Additional, free style feedback	Textbox	Free text, optional

6.4.3 *Methods and Timing of Assessing, Recording and Analyzing Variables*

Once the last patient will have completed the study and all the queries have been resolved, database will be locked, cleaned and exported for final statistical analysis. Study report will be issued following final database lock.

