6.6 Study related Procedures

6.6.1 General

The potential candidates will be screened to assess whether they are appropriate candidates for inclusion in this study. Informed consent will be obtained prior to initiation of any of the following clinical procedures that are performed solely for the purpose of determining eligibility for research. Pregnancy test for female patients with childbearing potential will be performed. The patient medical history, migraine history and diagnosis will be recorded and verified, the use of concomitant medication will be recorded in designated case report forms. Eligible patients will receive a documented training, and upon its successful completion the investigational device will be handed to study participants for home use. As per the IFU, participants are instructed to activate the device at the onset of a migraine headache and manually adjust stimulation intensity to a level where it is perceivable but not painful. Participants are requested to refrain from use of rescue medications prior to and during the first two hours after treatment and, if could not comply with this, record their use in the cellular application. Via the smartphone application, each participant will be asked to rate his/her migraine pain level three times: (1) upon starting the treatment, (2) two hours after treatment, (3) 48 hours after first treatment corresponding to the current migraine attack, using Pain Grades Scale (0 - no pain, 1- mild pain, 2- moderate pain, 3 – severe pain). At the end of each treatment, participants will be asked to provide feedback using the application regarding the time elapsed from start of migraine attack to start of the treatment, their use of medication. In case of failure to provide feedback regarding pain level post-treatment, telephone follow-up will be performed by study investigator staff to solicit such feedback. Additional migraine symptoms will be self-reported using the application. Follow up phone calls will be scheduled to record change in medical condition, concomitant medication and migraine therapy. Unscheduled visits will be recorded and termination visit will be scheduled upon the completion of the study as defined by treatment of four qualifying attacks over the course of two months (whichever is achieved first). In the event of premature discontinuation an early discontinuation visit will be scheduled.

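### The documents disagree on the activation trigger, the elapsed-time clock and the start-of-treatment pain scale, so an attack treated before pain could not be recorded as such yet could count as a success

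*Combined protocol and SAP*

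**What the plan says.** **Trigger.** The Synopsis (Study Design, Stage Two) says "Subjects will be asked to apply the device and administer treatment at onset of their migraine pain". Section 6.6.1, citing the instructions for use, says "participants are instructed to activate the device at the onset of a migraine headache". Sections 3.6 and 5.2 also refer to onset of a headache. The Synopsis (Study Procedures) instead says "Participants will be instructed to activate the device at the onset of a qualifying migraine attack", and section 6.1 (Stage Two) says "Participants will be instructed to activate the device at onset of a qualifying migraine attack".

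**Clock.** The Synopsis (Study Procedures) asks for the "time elapsed from start of migraine attack to start of the treatment"; 6.1 and 6.6.1 use the same reference point. The start screen in 6.4.2.1 has the item "Time from onset of migraine pain", with under 10 minutes as its lowest category.

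**Scale at treatment start.** Section 6.1 specifies the "Pain Grades Scale (0 - no pain, 1- mild pain, 2- moderate pain, 3 – severe pain): (1) upon starting the treatment". The Synopsis (Study Procedures) and 6.6.1 also give 0–3. The start screen lists "Mild (1), Moderate (2), Severe (3") and nothing lower. The 2-hour and 48-hour screens offer all four grades.

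**Endpoints.** The primary variable (7.2.1) is 1 if the subject has pain grade 0 at 2 hours, without rescue medication, in at least 50% of treated attacks. It sets no condition on pain at the start. Secondary endpoint 1 (6.3.2) does use the starting grade: moderate or severe must fall to mild, and mild must fall to none. It has no rule for a start at grade 0.

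**The concern.** Patients with aura are eligible (6.5.1, criterion 2). For them the attack can begin before the pain does, so the two trigger wordings can give different activation times. A participant who follows 6.1 literally could activate the device with no pain.

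The start screen cannot record that state. The participant would have to choose grade 1, 2 or 3, or leave the item blank. Being pain-free at 2 hours means something different for an attack that had no pain to relieve, yet the primary variable does not separate the two cases. Participants enter these data themselves, so information not captured at the time may not be recoverable.

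**Working it through.** The check is mainly textual: the passages set side by side, then an attack without pain at start followed through the scoring rules.

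**1. Passages compared**

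| Place | Activate at onset of | Clock starts at | Pain grades at start |
|---|---|---|---|
| Synopsis, Study Design | pain | – | – |
| Synopsis, Study Procedures | qualifying attack | attack | 0–3 |
| 3.6 and 5.2 | headache | – | – |
| 6.1, Stage Two | qualifying attack | attack | 0–3 |
| 6.6.1 | headache | attack | 0–3 |
| 6.4.2.1, start screen | – | pain | 1–3 |

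The disagreement between text and screen on the scale and the clock stands whichever trigger was meant.

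**2. Can such an attack be identified later?** The start screen holds pain grade, time from pain onset, nausea, photophobia, phonophobia and allodynia. It has no grade 0, no category for pain not yet begun, and no aura item. A blank grade would look like any other missing entry. The 2-hour and 48-hour screens have an optional free-text box, where a participant might volunteer the fact, but nothing asks for it.

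**3. How the attack would score**

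- Primary (7.2.1): only the 2-hour grade and rescue use matter. No pain at 2 hours and no rescue is a success, whatever was entered at the start.
- Secondary 1 (6.3.2): if entered as mild, with no pain at 2 hours and no rescue, it is a response.

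**4. Invented examples of the effect on one subject**

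- Four treated attacks. Two start with pain and fail; two start without pain, stay painless and need no rescue. Under 7.2.1: 2/4 = 50%, responder. Counting only attacks with pain at start: 0/2 = 0%, non-responder.
- Three treated attacks. One starts with pain and succeeds; two start without pain and have pain at 2 hours. Under 7.2.1: 1/3 = 33%, non-responder. Counting only attacks with pain at start: 1/1 = 100%, responder.

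So the effect on a subject's status can go either way.

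**5. The plan's sample size, and why it is not discounted here.** Inputs from 7.4 and 7.8.1: 30% against 10%, two-sided 5%, 80% power, 1:1. With p̄ = 0.20:

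n per arm = [1.96 × √(2 × 0.20 × 0.80) + 0.8416 × √(0.30 × 0.70 + 0.10 × 0.90)]² / 0.20² = (1.109 + 0.461)² / 0.04 ≈ 61.6, so 62 per arm and 124 in total.

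This reproduces the stated 124; power at 62 per arm is 80.3%. Adjusting it would need the share of attacks treated before pain and their 2-hour outcome by arm. The documents give neither.

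**The case against.** Most of the text presupposes pain. The Synopsis (Study Design), 3.6, 5.2 and 6.6.1 speak of pain or headache. Section 3 gives the rationale as a window at pain onset, and 6.1 defines a qualifying attack by prior freedom from headache. Both the pain and timing items on the start screen assume that pain has begun. No passage describes treatment during aura. On that reading, leaving out grade 0 is deliberate and a start without pain is outside the plan. This has weight, and it limits how common the problem is likely to be. It does not remove the instruction in 6.1 and the Synopsis (Study Procedures), nor the 0–3 scale stated for the start rating in three places.

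Two stronger readings are tempting and not supported.

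- A reader might infer that attacks treated before pain enter the pain endpoints as mild. No passage says so: the participant could choose another grade, leave the item blank or wait for pain. The starting grade does not enter the primary variable at all, so coding it as mild changes nothing there; it matters for secondary endpoint 1.
- A reader might infer that power falls below 80%, pointing to the pilot, where 40 + 11 = 51 of 69 + 17 = 86 participants (59%) had aura (4.2). That counts participants, not attacks treated before pain. The pilot also told participants to activate at attack onset and rated starting pain on a 0–10 scale; mean pain at activation was 4.6. A mean does not exclude some zeros, but it gives no sign that starts without pain were common. Because the pilot rates underlie the planning rates in 7.4, any such attacks may already be reflected in them.

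A last objection is that a grade 0 option is unnecessary if the passages are reconciled to pain onset, and would make room for unintended starts. Even then, it lets such a start be seen rather than hidden, and the baseline condition proposed below keeps it from counting.

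**Conclusion.** The point holds as an inconsistency in the instructions and data capture, combined with an endpoint rule that has no safeguard. The trigger, the clock and the start scale each differ between passages. Under the wording of 6.1, an attack begun without pain could not be recorded as such, could count as a success in the primary endpoint, could count as a response in secondary endpoint 1 if entered as mild, and could not be reliably identified afterwards.

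This rests on two things: patients with aura are eligible, and some of them may follow the attack-onset wording before pain begins. The frequency is unknown and may be low. No effect on power, on the sham response rate or on the direction of bias is claimed. The change is worth making because it is nearly free and the information may not be recoverable later.

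**What to change.** 1. Reconcile the Synopsis (Study Design and Study Procedures), 6.1, 6.4.2.1 and 6.6.1 on the activation trigger, the elapsed-time clock and the start-of-treatment scale. Which trigger applies is for the sponsor and investigators to settle; this review does not choose.
2. Make the start screen carry the 0–3 scale that 6.1 already states.
3. State in 7.2.1 and in 6.3.2 item 1 that a treated attack counts only if the pain grade at start of treatment is 1–3.
4. Tabulate any attacks started at grade 0 separately by arm, with their 2-hour outcomes.

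The cost is one dropdown value, a short endpoint rule in two places and one table. The downside is that any grade 0 attacks leave the denominator. A subject whose only treated attacks began at grade 0 would remain in the mITT set (7.7.2) with no countable attack, so the rule should also say how that subject is scored.
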